7. REGULATORY ISSUES	13
7.1. ETHICS APPROVAL	13
7.2. CONSENT	14
7.3. CONFIDENTIALITY	14
7.4. INDEMNITY	14
7.5. SPONSOR	14
7.6. FUNDING	14
7.7. AUDITS	14
8. STUDY MANAGEMENT	14
9. PUBLICATION POLICY	14
10. REFERENCES	15
11. APPENDICES	17
11.1. Client Satisfaction Questionnaire (CSQ-8)	17
11.2. Health literacy assessment	17
11.3. Knowledge and Perception Questionnaire	18

GLOSSARY OF ABBREVIATIONS

AE	Adverse Event
ANOVA	Analysis of Variance
CSQ	Client Satisfaction Questionnaire
DMSC	Data Monitoring and Safety Committee
GA	General Anaesthesia
ICH GCP	International Conference for Harmonisation of Good Clinical Practice
ITT	Intention To Treat
NVS	Newest Vital Sign
PI	Principal Investigator
PIS	Patient Information Sheet
RA	Regional Anaesthesia
REC	Research Ethics Committee
SAE	Serious Adverse Event
SSA	Site Specific Assessment
SVC	Standard Verbal Consent
TMG	Trial Management Group
VAC	Video Assisted Consent

KEYWORDS

Consent
Video
Anaesthesia
Regional
Satisfaction
Knowledge

STUDY SUMMARY

- TITLE** CIA: Consent in Anaesthesia
- DESIGN** Prospective randomised-controlled trial
- AIM** To determine whether presenting both techniques of general anaesthesia and regional anaesthesia in an unbiased manner, with video media, aids the anaesthetic consent process, compared to standard verbal consent alone.
- OUTCOME MEASURES** Primary outcome:
- Participants' satisfaction regarding the anaesthetic consent process
- Secondary outcomes:
- Knowledge, attitudes and practices towards anaesthesia
 - Participants' choice of anaesthetic technique
- POPULATION** General adult population (>18yrs), males and females
- ELIGIBILITY** Adult participants (>18yrs) who give written, informed consent.
- Exclusion criteria:
- Patients <18 years or vulnerable groups
 - Inability to communicate in English or language difficulty that requires an interpreter
 - Severe vision or hearing loss if lack of other communication channels
 - Private patients
 - Prisoners
 - Patients who reside outside the United Kingdom (home address)
 - Opt-out patients on GP register
- DURATION** 2 years

1. INTRODUCTION

Anaesthetists deliver just under 3 million anaesthetics in the United Kingdom every year^{1,2}. General anaesthesia (GA) and regional anaesthesia (RA) are both routinely used for intraoperative anaesthesia. The estimated annual numbers (with percentage of all cases) of GA, sedation and awake cases were 2 766 600 (76.9%), 308 800 (8.6%), and 523 100 (14.5%), respectively².

Regional anaesthesia with central neuraxial or peripheral nerve plexus blockade has a proven track record for success in surgery and several potential benefits. It may be undertaken with or without sedation. General anaesthesia is associated with greater immediate post-operative pain and opiate use³, whereas brachial plexus blockade may be associated with delayed rebound pain⁴. However, rebound pain may be modulated by an understanding of the dissipation of single-injection regional anaesthesia and attenuated by longer duration analgesia as well as multi-modal therapy^{5,6}. When regional anaesthesia has been used instead of general anaesthesia, the median time to hospital discharge is shortened and the in-hospital mortality is also decreased.

There are a number of surgical procedures which may be undertaken under either general anaesthesia or regional anaesthesia. The Association of Anaesthetists of Great Britain and Ireland guidelines on consent state that for a decision by an individual to be valid, it must have been undertaken voluntarily, without coercion^{8,9,10}. Although it may be good practice for the clinician seeking consent to indicate a preference for a therapeutic option, they should be aware that a vulnerable patient may feel coerced by the doctor's preference due to the imbalance of power and influence in the doctor-patient relationship. The anaesthetist seeking consent should be aware of this and not allow their preferences to override the patients autonomy^{8,11}. When these principles are applied to the type of anaesthesia (GA vs RA) offered, it stands to reason that both options of GA and RA should be offered to patients, if both are feasible options for the surgery to be undertaken. Barriers to this are multifactorial and the time pressures of a busy anaesthetic list should not be underestimated.

Video assisted consent (VAC) offers a potential way to improve doctor-patient communication and to improve the consent process when compared to standard verbal consent (SVC)¹². Hand-held, mobile media devices are becoming ever more prevalent and lend themselves to easy use within a busy hospital environment. The role of video-based education in the process of consent has shown promise in studies of surgical consent. Several studies have shown that video-based patient education have led to better patient comprehension and satisfaction as well as reduced patient anxiety during the consent process¹²⁻¹⁵. The acceptance of multimedia technology in preoperative surgical consent has been demonstrated across a spread of surgical disciplines, including ophthalmic surgery¹⁶⁻¹⁷, urological surgery¹², orthopaedic surgery^{15,18-19}, bariatric surgery²⁰ and vascular surgery²¹. The use of video-assisted consent for invasive procedures on the intensive care unit has also had positive results²².

The choice of general vs regional anaesthesia by a patient undergoing orthopaedic surgery has been demonstrated to change with patient education. In a randomised controlled trial in Cardiff, the use of informational internet web pages led to patients awaiting hip or knee arthroplasty altering their preferences from general anaesthesia to a neuroaxial technique²³. Preoperative patient education of the advantages of neuroaxial anaesthesia was also shown to be associated with a higher number of patients choosing a regional anaesthetic in the setting of total knee arthroplasty²⁴.

A tertiary centre trial in the UK demonstrated that patient recall of consent for regional anaesthesia was poorer than that for surgical consent²⁵. Video-assisted patient education during a preanaesthetic visit has been shown to lead to a better understanding of the procedure and risks of anaesthesia with no increase in patient anxiety²⁶. This suggests that more effective strategies for patient education with regards to regional anaesthesia and consent for regional anaesthesia are required and video-assisted methods are likely to be beneficial.

Patient and Public Involvement and Engagement (PPIE) work consisted of consulting 40 members of the multidisciplinary theatre team, including consultants, trainees, operating department practitioners and nurses. Although 92% of those surveyed had not used a video-assisted consent process before, 95% felt that a video-assisted consent process would be a useful tool. 88% of those surveyed had not used or seen any type of online consent tool but 92% voted that an anaesthetic online consent process would be useful. The team has also spoken to patients and lay public who have also felt that a video-assisted consent process would help with their understanding and satisfaction of the consent process should they need to have an anaesthetic for surgery.

The COVID pandemic has brought about changes in pre-operative assessment and anaesthetic consent²⁷. The need for social distancing has meant that family and friends are often no longer able to be present when the patient meets the anaesthetist on the day of surgery to discuss the anaesthetic process and options; as well as to obtain anaesthetic consent. The videos created specifically for video-assisted anaesthetic consent could not only be used to allow the patient to review the anaesthetic process in advance of the anaesthetic consent to allow time for informed consent, they could also be reviewed with family and friends that the patient may depend on for support and advice

2. STUDY OBJECTIVES

- The aim of this study is to determine if the use of video assisted consent during the anaesthetic consent process, for both GA and RA, affects the participants' satisfaction, knowledge of, and attitudes towards, anaesthesia.
- We hypothesise that using video media will improve participant knowledge, understanding and satisfaction of the anaesthetic consent process, thereby resulting in better quality informed consent.

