3.4. PROTOCOL

Recruited participants will be randomised into two groups. The control group will undergo the standard video verbal consent process for both GA and RA for orthopaedic surgery. This will be delivered using a standardised video script that will be generated from existing certified material, as well as being reviewed by an experienced body of anaesthetists, in order to ensure that the length and content of information given is appropriate, unbiased, accurate and consistent. In order to account for adaptations to services in light of the coronavirus pandemic, and to further ensure standardisation, this verbal communication will be pre-recorded and shown to the participant. The intervention group will also be shown the same pre-recorded standard verbal consent, but following this will additionally be shown a specifically recorded video of the anaesthetic process for both GA and RA. This video will aim to communicate the same information as that found in the traditional verbal consent, using an actor undergoing an anaesthetic to provide context.

Following the consent process, participants from both groups will be asked to complete two questionnaires to enable assessment of participant satisfaction, retained knowledge and perceptions regarding anaesthesia from the consent process, and a stated preference for anaesthetic technique (i.e. GA or RA).

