6. STATISTICS AND DATA ANALYSIS

Two hundred and six patients in total will be randomised using an online randomisation tool. <https://www.graphpad.com/quickcalcs/randomize1.cfm>

Patient satisfaction, the primary endpoint measured by CSQ-8, is expected to be approximately 30 in both arms. VAC and SVC will be considered equivalent if the VAC satisfaction score is no more than 1.5 points lower than the SVC score. With 103 subjects in the Control Group (SVC) and 103 subjects in Experimental Group (VAC), there is an 85% chance that the observed difference (SVC-VAC) in satisfaction scores will be significantly less than 1.5 at the 5% level, if the true means are 30 in both groups. The standard deviation has been assumed to be 4.

After the first 50 participants have been entered into the trial a feasibility analysis will be undertaken. Three outcomes of particular interest will be the accrual rate, the proportion accepting their randomisation and the proportion evaluable (completing all questionnaires). With 50 participants it will be possible to estimate the proportions in the latter two groups with 95% confidence intervals of at most $\pm 15\%$. A record will be kept of the number of participants approached and their reasons for declining to enter the study. With 50 participants it should be possible to identify and remedy any minor issues that are impediments to recruitment. It may be necessary to plan to increase accrual if withdrawals or the number of non-evaluable participants is greater than expected.

The primary analysis will be by intention to treat (ITT). It is planned to make comparisons between groups for normally distributed variables with independent samples t-test or ANOVA, variables that are not normally distributed will be analysed with Mann–Whitney U-tests. The Chi-squared or Fisher's exact test will be used to compare proportions and Pearson Product or Spearman Rank statistics will be used to assess correlation. Multiple regression exploratory analyses may be employed to estimate multiple effects simultaneously.

Data and all appropriate documentation will be stored for a minimum of 5 years after the completion of the study, including the follow-up period.

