11. APPENDICES

11.1. CLIENT SATISFACTION QUESTIONNAIRE (CSQ-8)

The Client Satisfaction Questionnaire (CSQ) instruments are self-report questionnaires constructed to measure satisfaction with services received by individuals²⁹.

The CSQ-8 is an 8-item questionnaire that measures the most salient items for the measurement of satisfaction with services:

Questionnaire Item	Scoring			
	4	3	2	1
How would you rate the quality of the service you received?	Excellent	Good	Fair	Poor
Did you get the kind of service you wanted?	Yes definitely	Yes generally	No not at all	No definitely not
To what extent has our service met your needs?	Almost all met	Most met	Only a few met	None met
If a friend were in need of similar help would you recommend our service?	Yes definitely	Yes I think so	No I do not think so	Definitely not
How satisfied are you with the amount of help you received?	Very satisfied	Mostly satisfied	Indifferent	Quite dissatisfied
Have the services you received helped you to deal more effectively with your problems?	Yes a great deal	Yes somewhat	No did not help	No made it worse
In an overall sense, how satisfied are you with the service you have received?	Very satisfied	Mostly satisfied	Indifferent	Quite dissatisfied
If you were seeking help again, would you come back to our service?	Yes definitely	Yes I think so	No I do not think so	No definitely not

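### The satisfaction criterion is one-sided non-inferiority labelled 'equivalent', and no test is assigned to CSQ-8 for the hypothesis that video improves satisfaction.

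*Combined protocol and SAP*

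**What the plan says.** Section 2 (Study objectives) opens with a non-directional aim: "The aim of this study is to determine if the use of video assisted consent during the anaesthetic consent process" affects satisfaction, knowledge and attitudes. It then gives a directional hypothesis: "We hypothesise that using video media will improve participant knowledge, understanding and satisfaction of the anaesthetic consent process".

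Section 6 (Statistics and data analysis) takes no improvement as its planning assumption: "Patient satisfaction, the primary endpoint measured by CSQ-8, is expected to be approximately 30 in both arms". The decision rule is "VAC and SVC will be considered equivalent if the VAC satisfaction score is no more than 1.5 points lower than the SVC score". The power statement is that "there is an 85% chance that the observed difference (SVC-VAC) in satisfaction scores will be significantly less than 1.5 at the 5% level", with 103 per arm, true means of 30 in both groups and an SD of 4. Whether the 5% is one-sided or two-sided is not stated.

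The analysis paragraph of Section 6 lists tests by type of variable: t-test or ANOVA if normally distributed, otherwise "variables that are not normally distributed will be analysed with Mann–Whitney U-tests". It names no test for CSQ-8 and does not mention the 1.5-point margin.

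On the interventions, Section 3.4 says: "The intervention group will also be shown the same pre-recorded standard verbal consent, but following this will additionally be shown a specifically recorded video". On the scale, Appendix 11.1 says: "The CSQ-8 is an 8-item questionnaire that measures the most salient items for the measurement of satisfaction with services". Each item is scored 1 to 4, so the total runs from 8 to 32.

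**The concern.** Three parts of the plan do not fit together.

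- **Label and rule.** Equivalence needs a limit on both sides. The rule limits only how much lower VAC may be, which is non-inferiority. A report that follows the plan could claim equivalence from a test that looked at one side.
- **Rule and hypothesis.** Section 2 expects better satisfaction. The only sized criterion assumes equal means and asks whether VAC is not much worse. VAC is the control recording plus a further video, so showing that it is not much worse leaves the hypothesis unanswered.
- **Rule and analysis.** The analysis paragraph does not say which test judges the 1.5-point criterion or which one tests for improvement. If CSQ-8 is not normal, the general rule sends it to a rank test, which does not estimate a difference in means.

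At stake is what the trial may conclude on its primary endpoint, and whether the test behind that conclusion is fixed before the data are seen. The knowledge part of the hypothesis is not affected.

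**Working it through.** **Inputs.** From Section 6: n = 103 per arm, SD 4, margin 1.5, true difference 0, 5% level, 85% power. From Appendix 11.1: range 8 to 32. The gains of 0.5, 1.0 and 1.5 points in step 4 are my assumptions; the plan gives no superiority effect.

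**1. Reproduce the stated figure.** SE = 4 × √(2/103) = 0.557, with 204 degrees of freedom.
- Sample size, one-sided 5%: 2 × 4² × (1.645 + 1.036)² / 1.5² = 102.2, so 103 per arm.
- Power with 103 per arm, noncentral t with parameter 1.5/0.557 = 2.69: 85.0%. This matches the plan.

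Other readings do not match:
- Non-inferiority at one-sided 2.5% would need 128 per arm.
- Two-sided equivalence (90% CI inside ±1.5) at equal means has power 2Φ(2.691 − 1.645) − 1 = 70.5% by normal approximation, and 70.1% by simulation. It would need about 136 per arm for 85%.

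So the figure is a one-sided 5% non-inferiority calculation. The sidedness is inferred from this match.

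**2. What meeting each criterion requires.**
- Non-inferiority: observed VAC-SVC above −1.5 + 1.652 × 0.557 = −0.58.
- Superiority, two-sided 5%: observed VAC-SVC above 1.972 × 0.557 = +1.10.

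Any result between −0.58 and +1.10 meets the sized criterion without showing improvement.

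**3. Likely shape of CSQ-8.** The expected mean lies (32 − 30)/4 = 0.5 SD below the maximum. A normal distribution with these values would put 1 − Φ(0.5) = 31% of scores above 32, which is impossible. If mean 30 and SD 4 are about right, the scores cannot be close to normal, and the switch to Mann–Whitney is likely to apply.

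I checked whether a mean-based analysis still works, under one assumed ceiling-heavy shape (8 plus a beta-binomial on 24, SD 4). The 90% CI kept about 85% power at equal means and declared non-inferiority in about 5% of trials at a true deficit of 1.5.

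**4. Superiority power with 103 per arm, two-sided 5%.**
- SD 4 in both arms: 14% for a gain of 0.5 and 43% for a gain of 1.0.
- For a gain of 1.5 the VAC mean is 31.5, and the largest SD the scale allows is √((32 − 31.5)(31.5 − 8)) = √11.75 = 3.43. SD 4 is therefore impossible in that arm. With control SD 4, power is 82% at a VAC SD of 3.43, 86% at 3 and 89% at 2.5 (t approximation). The extreme two-point VAC distribution gave 80%. A fair statement is roughly 80–90%.

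**5. Alpha for a superiority step.** A 95% CI wholly above 0 forces the 90% lower limit above 0, hence above −1.5. Superiority cannot be shown without non-inferiority, so testing it second costs no alpha.

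**The case against.** The case for leaving the plan alone has force. The sample-size arithmetic is right for the rule stated. The sentence that uses the word 'equivalent' also defines it, so a careful reader knows what is meant. The t-test and Mann–Whitney test in Section 6, in their ordinary form, test for a difference, which fits the non-directional aim in Section 2. All of that stands. What remains is that the label claims more than the rule can show, and that no listed test is tied to CSQ-8, to the margin or to the hypothesis.

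Four stronger readings are tempting and are not supported:
- *No superiority test is available.* One could be drawn from the generic list; the gap is that it is not designated.
- *The trial is short of power for a 1.5-point gain, with 76% against the stated 85%.* The 76% comes from moving from one-sided to two-sided 5% and uses SD 4 in a VAC arm where the scale forbids it. At feasible SDs the power is roughly 80–90%. A larger sample computed on the same SD has no basis either.
- *1.5 points is the gain that the plan regards as meaningful.* In Section 6 it is a tolerated loss.
- *The rank test would inflate false non-inferiority by a known amount.* The plan never describes a Mann–Whitney test against the margin, and any rate depends on an assumed score distribution. Only the qualitative mismatch follows from the text.

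**Conclusion.** The point holds as an inconsistency between Sections 2 and 6, and as an unassigned primary analysis. It is not an error in the sample size. Section 6 labels as equivalence a lower-side criterion whose 85% is non-inferiority power at one-sided 5%; true equivalence would have about 70%. Meeting the criterion does not support the hypothesis of improved satisfaction, and the comparison that could support it is not designated for CSQ-8. The likely skew would also lead to a test that cannot be read against the margin.

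This should be fixed before analysis because it changes what the trial may claim. Confidence is high on the label, the reproduced power and the missing assignment. The expectation of skew rests on the plan's own mean, SD and scale maximum. The superiority power figures rest on assumed gains.

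**What to change.** Keep 206 participants and change the wording:

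1. In Section 6 replace 'equivalent' with 'non-inferior' and state the one-sided 5% level. Declare non-inferiority if the lower limit of the two-sided 90% CI for the CSQ-8 mean difference (VAC-SVC) is above −1.5.
2. Name a superiority test of the same mean difference (two-sided 95% CI above 0), carried out after non-inferiority is shown. Allow a claim of improved satisfaction only if it succeeds.
3. Analyse CSQ-8 by the mean difference whatever its normality, with a rank test as supportive only.
4. Reword the satisfaction part of Section 2 to match: VAC is non-inferior to SVC on CSQ-8 with margin 1.5, and whether it improves satisfaction is also tested.

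If superiority power is stated, give it as two-sided 5% for assumed gains: about 14% at 0.5 and 43% at 1.0 with SD 4, and roughly 80–90% at 1.5 depending on the SD in the VAC arm.

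The cost is an amendment of text, with no extra participants, data or alpha. The downside is that a mean-based test may lose some power against a rank test if CSQ-8 is strongly skewed.

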3. RESEARCH PLAN AND METHODOLOGY

3.1. STUDY POPULATION

Study centre(s)

- Imperial College Healthcare NHS Trust

Study sample

- 206 participants

Inclusion criteria

- ≥ 18 years
- Presenting to pre-operative orthopaedic surgical clinic
- Informed consent

[figure not shown]
Exclusion criteria

- Patients <18 years or vulnerable groups
- Inability to communicate in English or language difficulty that requires an interpreter
- Severe vision or hearing loss if lack of other communication channels
- Private patients
- Prisoners
- Patients who reside outside the United Kingdom (home address)
- Opt-out patients on GP register

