3.3. RECRUITMENT

Potential trial participants will be recruited from the general adult population (i.e. males and females aged over 18yrs) presenting to pre-operative orthopaedic surgical clinic within Imperial College Healthcare NHS Trust at St Mary's and Charing Cross Hospitals. Potential participants will be approached by members of the study team that may or may not be part of the primary care team. All potential participants will be invited to take part with the use of a participant information sheet (PIS), approved by a Research Ethics Committee, that describes the study. The participant will have time to read the PIS and to discuss their participation with others outside the research team (e.g. relatives or friends) if they wish. A

member of the research team will then answer any questions, confirm the participant's eligibility and take written informed consent if the participant decides to proceed. Details of all participants approached for the trial and reason(s) for non-participation (e.g. reason for being ineligible or patient refusal) will be documented. Also the non-participant does not need to give a reason for non-participation and if so will be documented as non-participation in the reason(s) for refusal. All data will be anonymised.

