11.3. KNOWLEDGE AND PERCEPTION QUESTIONNAIRE

SECTION1: PREVIOUS EXPERIENCE

1. Have you been anaesthetised before? Yes ___ No ___
 - 1.1 If so, what type (or types) of anaesthesia?

General anaesthesia ____
 Spinal or epidural (lower half of the body) ____
 Nerve block (for example only arm, hand or foot anaesthesia) ____
 Local anaesthesia ____

2. If you have been anaesthetised, have you experienced any complication related to anaesthesia?
 Yes ____ What?

No ____
 I have never been anaesthetised ____

3. Do you know anyone who has experienced complications related to regional anaesthesia?
 Yes ____ What?

No ____

SECTION 2: KNOWLEDGE OF ANAESTHESIA

4. How many options do you have for your anaesthetic for your operation?
 0 ____ 1 ____ 2 ____ More than 2 ____ Don't Know ____

5. Having which type of anaesthetic will mean that you are awake for your surgery?
 General ____ Regional ____ Both ____ Don't Know ____

6. Which type of anaesthetic is associated with the following statements:
- | | |
|--------------------------------------|--|
| A cannula is inserted into your hand | General ____ Regional ____ Both ____ Don't Know ____ |
| Monitors are applied to your body | General ____ Regional ____ Both ____ Don't Know ____ |
| A tube is inserted into your throat | General ____ Regional ____ Both ____ Don't Know ____ |
| You can listen to your own music | General ____ Regional ____ Both ____ Don't Know ____ |
| You will have a heavy, numb arm | General ____ Regional ____ Both ____ Don't Know ____ |

7. When having **general anaesthesia**, how common is it to experience each one of the following events?

How common is it to:	Very rare	Rare	Uncommon	Common	Very Common
Experience nausea or vomiting	1	2	3	4	5
Have a sore throat	1	2	3	4	5

Suffer confusion, disorientation or memory loss	1	2	3	4	5
Experience pain whilst having the anaesthetic	1	2	3	4	5
Feel anything during surgery	1	2	3	4	5
Have damage caused to your teeth	1	2	3	4	5
Have permanent nerve damage	1	2	3	4	5
Suffer a life-threatening event	1	2	3	4	5
Be aware of your surroundings during surgery	1	2	3	4	5

8. When having **regional anaesthesia (nerve block)**, how common is it to experience each one of the following events?

How common is it to:	Very rare	Rare	Uncommon	Common	Very Common
Experience nausea or vomiting	1	2	3	4	5
Have a sore throat	1	2	3	4	5
Suffer confusion, disorientation or memory loss	1	2	3	4	5
Experience pain whilst having the anaesthetic	1	2	3	4	5

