Having damage caused to your teeth	1	2	3	4	5
Having permanent nerve damage	1	2	3	4	5

Suffering a life-threatening event	1	2	3	4	5
Being aware of your surroundings during surgery	1	2	3	4	5

SECTION 4: PRACTICES TOWARDS ANAESTHESIA

16. Which option for anaesthesia would you choose for your surgery?

General anaesthesia ____ Regional anaesthesia ____

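### Neither planned operation nor limb is recorded at baseline, yet questionnaire item 4 and the numb-arm line of item 6 have correct answers that depend on them

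*Combined protocol and SAP*

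**What the plan says.** **Who enters.** The inclusion criteria in section 3.1 are age, consent and "Presenting to pre-operative orthopaedic surgical clinic". Section 3.3 adds that "Potential trial participants will be recruited from the general adult population" attending that clinic at two hospitals. None of the exclusions in section 3.1 or the Study Summary concerns the operation, the limb, or which techniques are possible.

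**What the rationale assumes.** The Introduction says "There are a number of surgical procedures which may be undertaken under either general anaesthesia or regional anaesthesia", which implies that not all can be. It holds that both should be offered "if both are feasible options for the surgery to be undertaken".

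**What is recorded at baseline.** Sections 3.5, 3.5.1 and 5 list age, gender, ethnicity, education level and the health literacy score. Operation and limb are not listed.

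**What is asked afterwards (appendix 11.3).**
- Item 4: "How many options do you have for your anaesthetic for your operation", with responses 0, 1, 2, more than 2, or don't know.
- Item 6, last line: "You will have a heavy, numb arm", with responses general, regional, both, or don't know.
- Items 8 and 12 gloss regional anaesthesia (RA) as nerve block, whereas item 1.1 lists spinal or epidural separately from nerve block.
- Item 16: "Which option for anaesthesia would you choose for your surgery", with general anaesthesia (GA) or RA as the only responses.

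No answer key, scoring rule or handling of inapplicable items is given.

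**The concern.** Knowledge is part of the hypothesis in section 2 and a named secondary outcome. Item 4 sits in the knowledge section, but its right answer belongs to the individual. A participant whose operation allows one technique is correct to tick 1, and a participant with two is correct to tick 2. A single key marks one of them wrong.

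The arm line has a similar fault. Lower-limb patients are foreseeable, because the Introduction itself cites hip and knee arthroplasty with neuraxial techniques. Such a participant, thinking of their own care, may find that neither technique gives a numb arm, and there is no box for that.

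Item 16 is also tied to the participant's own surgery. If people without a real alternative respond less to the video, the difference between arms in the proportions choosing GA or RA shrinks. Without operation and limb in the dataset, none of this can be scored properly or examined later.

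**Working it through.** **1. The plan's own sample size (section 6).** Inputs: margin 1.5, SD 4, true difference 0, 5% level, power 85%.

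n per arm = 2 × 4² × (1.645 + 1.036)² / 1.5² = 102.2, rounded up to 103, so 206 in total. Power at 103 per arm = Φ(1.5 / 0.5574 − 1.645) = 85.2%, where 0.5574 = 4 × √(2/103).

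The stated figure reproduces as a one-sided 5% non-inferiority calculation. It rests on the satisfaction score alone, so nothing in this point changes it. The documents state no power for knowledge or choice.

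**2. How much of the knowledge section depends on the operation.** Scorable responses in section 2 of the questionnaire: item 4 (1) + item 5 (1) + item 6 (5) + item 7 (9) + item 8 (9) + item 9 (5) = 30. Item 4 and the arm line are 2 of 30, or 6.7% of the maximum if every response counts equally. Equal weighting is an assumption, since no scoring rule is given. The nine lines of item 8 are touched less directly: a patient whose RA would be spinal can still answer them about nerve blocks in general.

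**3. Possible dilution of the choice comparison (illustration only).** Four inputs are assumptions not found in the documents:
- the share f of participants with one feasible technique (0 to 30%);
- a 20-point true difference among the rest;
- the base rate;
- no video effect at all in the single-technique group.

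The test is two-sided at 5%. With all 206 kept, the difference is 20 × (1 − f) points. With proportions near 50%, SE = √(0.5/103) = 0.0697 and power = Φ(difference/SE − 1.96). Restricting to dual-option participants keeps 20 points but cuts n per arm to about 103 × (1 − f), with SE = √(0.5/n).

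| f | Diluted difference | Power, all 206 | n per arm if restricted | Power, restricted |
|---|---|---|---|---|
| 0% | 20 points | 81.9% | 103 | 81.9% |
| 10% | 18 points | 73.4% | 93 | 77.9% |
| 20% | 16 points | 63.2% | 82 | 72.6% |
| 30% | 14 points | 52.0% | 72 | 67.0% |

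Using 30% v 50% choosing RA, with the pooled SE under the null, the figures for all 206 are 83.9, 75.8, 66.0 and 54.9%. Restricted, they are 83.9, 80.0, 74.8 and 69.1%.

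The fair measure of what a restricted analysis recovers is the gap within each row: 4.5, 9.4 and 15.0 percentage points near 50%. The fall from 81.9% overstates it, because restriction also loses participants.

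**The case against.** Several objections carry weight.

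- **The choice outcome is hypothetical.** Sections 3.4, 3.5.2 and 5 treat it as a stated or theoretical preference, not the technique received. A reader might infer that item 16 has no valid answer for single-technique patients. The documents do not support that: anyone can state a preference.
- **Item 4 offers 1 and don't know.** A single-technique patient can answer truthfully. The fault is the missing participant-specific key.
- **The arm line can be read as recall.** Sections 3.4 and 5 base the questionnaire on the content of the consent process, and both arms see the same verbal recording. The script is not in the documents, so whether it uses an arm block as its example cannot be told.
- **Dilution is not shown.** Nothing says participants are told that only one technique is feasible, so their preference might shift like anyone else's.
- **Broad eligibility is defensible.** A reader might infer from "both options of GA and RA should be offered to patients, if both are feasible options for the surgery to be undertaken" that the trial should admit only patients with both options. That sentence describes good consent practice and is not an eligibility rule. A pragmatic sample suits a generic consent tool, and judging feasibility before randomisation may need a competent assessor.
- **Some information exists.** Item 4 itself and the free-text reason after item 16 hint at perceived options. Both are collected after the intervention and may be affected by it, so they cannot replace a baseline field.

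These points narrow the concern to scoring, interpretation and missing baseline data. They do not remove it: item 4 still lacks a common key, the arm line still lacks a neither response, and operation and limb are still not listed for collection.

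**Conclusion.** The point holds as a weakness in secondary outcomes. Item 4 has no single correct answer across the sample, the arm line may not describe RA for lower-limb patients, and the planned data cannot identify who is affected. That puts noise into 2 of 30 knowledge responses under equal weighting, and it may dilute the stated-preference comparison.

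The size of any dilution is unknown, because the documents give no share of affected patients. The power figures above hold only under the assumed share, effect, base rate and zero response in the single-technique group.

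A reader might go further and infer bias between the arms or an underpowered primary analysis. Neither follows. Randomisation spreads these patients evenly in expectation, and the 206 depends only on the satisfaction score. Figures in the protocol were not available to check, so the conclusion rests on the text.

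**What to change.** 1. Record planned operation and limb at baseline, before randomisation, from the clinic listing. Add both fields to sections 3.5, 3.5.1 and 5.
2. Score item 4 against the planned operation, or leave it out of the knowledge score. State which in section 6.
3. Make the arm line site-neutral, for example *the part of your body being operated on will be heavy and numb*, or add a neither response. Check the wording against the consent script, and check the nerve-block gloss in items 8 and 12 at the same time.
4. Keep item 16 in all participants as the main choice analysis. Prespecify a sensitivity analysis in participants whose listed operation is one usually done under either technique, with the list of operations fixed before the data are examined by arm.

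Eligibility can stay as it is. The cost is one or two baseline fields, one reworded item and a smaller denominator in the sensitivity analysis.
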